Study IV is a feasibility study testing the developed intervention for feasibility and acceptability in a small sample (N=30) of patients with IBD from the gastroenterology outpatient clinic at Bispebjerg Hospital, Copenhagen. By conducting a feasibility study with a small sample size, we want to follow the course of an intervention that has been developed as an individual offer with possibilities and solutions for the individual patient, but still operated within a controlled and standardized research frame. Thus, before testing the intervention in a large-scale randomized controlled trial, we need to evaluate whether this model is applicable in the patients and their individual settings. Assessment of feasibility will include identification of barriers for recruitment, acceptance of group/randomization status, delivery methods, retention, outcome assessments and logistics using qualitative and quantitative methods for process evaluation (19).

In – and exclusion criteria

The inclusion criteria for patients:

- A diagnosis of IBD (Crohn's disease or ulcerative colitis) > 1 year
- > 18 years of age
- Minimum three months stable medication type and dose without use of steroids as part of the medical treatment during the last three months
- Speak and understand Danish

The exclusion criteria for patients:

- Unable to give informed consent
- Active inflammatory disease in joints, skin, pancreas, thyroid, lungs or liver that can hinder engagement in physical activity and exercise
- Cognitive and/or mental disabilities that can hinder engagement in physical activity and exercise
- Engaging in high-intensity physical activity -/> 8 hours pr week

Recruitment

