Patients for the feasibility study will be recruited from the gastroenterology outpatient clinic at Bispebjerg Hospital, Copenhagen. Patients will be identified and invited by nurses and physicians at the outpatient clinic, who will describe the project and provide patients with written information about the project. If identified patients are willing and eligible to participate according to in – and exclusion criteria, the outpatient clinic staff will pass on the patients' contact details to intervention leader, TT, or a project nurse, employed at the gastroenterology department. Either TT or the project nurse will then contact the patients by telephone and invite them and a relative (if wished for) to an information meeting at the gastroenterology department. Here, the patients will receive oral information on the project by TT in a private room. This information will include the purpose, methods, time frame and possible risks of participating with sufficient time for the patients to understand and ask questions. Furthermore, the patients will be informed about the possibility of declining any new information on their health status that may emerge during the study, and additionally, the possibility to withdraw their consent at any time without it affecting their current treatment in the clinic. If patients decide to participate in the study during the information meeting, they will sign a written consent. However, patients will also be offered 48 hours

to reflect and decide on participation or not. Either TT or the project nurse will then obtain their signed consent at a later stage in the clinic.

Randomization and blinding

Study participants will be randomly assigned (1:1) to either an intervention group (n=15) or a control group (n=15). The randomization will be conducted through the REDCap (Research Electronic Data Capture) platform (see description under 'data management'). The allocation sequence will be concealed from the project leaders. It will not be possible to blind participants and project staff delivering the intervention to allocation status, whereas all outcome data will be collected by blinded outcome assessors.

Intervention

The intervention is an individually tailored, behavioural intervention addressing the individual patient's knowledge, motivation, resources and opportunities for increasing daily physical activity in the individual's everyday life.

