The main setting of the intervention will be the participants' everyday lives (family, work/school, leisure-time activities). However, the Gastroenterology Department, Bispebjerg Hospital, and potentially, local municipal health centres and sports clubs will be the actual physical places for the specific intervention elements (e.g. education, counselling sessions, physiotherapist-led sessions, exercising in small communities ('exercise buddies')). As the intervention focuses on and takes place in an 'everyday life'

setting, we expect the intervention to be realistic and implementable in the gastroenterology clinic and/or the municipal health centres subsequently.

Control group

Participants randomized to the control group will be encouraged to maintain their usual lifestyle and activities. They will be expected to undergo the same baseline – and outcome assessment as the participants in the intervention group.

Outcome measures

The primary focus of the study is to investigate study feasibility and acceptability, including investigating facilitators/barriers for recruitment, acceptance of group allocation, study retention, the quality of delivery methods, intervention fidelity (project staff's fidelity to intervention manual), participants' perception of the developed intervention and the adherence to outcome assessments. Assessment of intervention fidelity and acceptability will include qualitative methods such as observations of the intervention elements and interviews with participants and project staff. The specific outcome assessments in the feasibility study will include a range of both objectively measured outcomes and self-administered questionnaires.

Objectively measured physical activity

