A venous blood sample will be drawn (not fasting). Total cholesterol, high-density lipoprotein cholesterol (HDL), and triglycerides will be measured. Low-density lipoprotein cholesterol (LDL) and very low-density lipoprotein cholesterol (VLDL) will be calculated by the formulae: $VLDL = \text{Triglyceride} \times 0.45$ and $LDL = \text{Total cholesterol} - HDL + VLDL$. In addition, C-reactive protein (CRP), albumin and glycosylated hemoglobin, type A1c (HbA1c) will be measured.

Blood pressure

Blood pressure will be measured, after 5 to 10 minutes of rest, 3 times at the right upper arm (average of the 3 measurements) with the participant in a sitting/lying position.

Anthropometric measures

Anthropometric measures such as height, weight and waist- and hip circumference will likewise be included in the assessments. Height is measured without shoes to the nearest centimeter; weight is measured in light clothing without shoes to the nearest 0.1 kg; waist circumference is measured midway between the lower rib margin and the iliac crest to the nearest 0.5 centimeter, without any pressure to the skin and with an unstretched tape measure; hip circumference is measured at the point yielding the maximum circumference over the buttocks to the nearest 0.5 centimeter. The tape should be held in a horizontal plane touching the skin but not indenting the soft tissue. Body mass index (BMI, kg/m²) and waist-hip ratio will be calculated.

Demographic and clinical information

In addition, information regarding demographics (e.g. sex, age, education, civil status, employment) and lifestyle (smoking and alcohol consumption) will be obtained by self-reports while data on disease location

and duration, disease severity, surgery, medical treatment and active co-morbidities in form of disease in joints, skin, pancreas, thyroid, lungs or liver and prescriptions (FMK) will be collected from Epic (Sundhedsplatformen). The researchers' direct access to the electronic patient records and retrieval of these data will be depended on signed informed consent from the relevant participant. Information on diagnosis and medical treatment is necessary for identification and screening of the participants (see in- and exclusion criteria) before an eventual signing of informed consent.

Data collection from outcome assessments

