Outcome assessment will be conducted at study inclusion/baseline and repeated at end of the intervention period (20 weeks (five months) from baseline) for each of the 30 participants. Participants will complete self-administered questionnaires regarding demographics, lifestyle, physical activity, disease-specific quality of life, pain, fatigue and intrusiveness of IBD. Anthropometric measures, blood pressure, fecal calprotectin test and a single blood sample will be obtained at the same time points by a project nurse. Calprotectin test and blood samples will be analyzed at Department of Clinical Biochemistry, Bispebjerg Hospital, for inflammation biomarkers and lipid status. In addition, the same project nurse will attach the SENS motion activity sensor on the participants' thigh and instruct participants how to wear the monitors 24 hours per day for seven continuous days. The activity sensors connect wirelessly to a smartphone application, and the recorded data are transmitted to the application every 10 minutes, when the smartphone is within network reach or stored on the sensor for later transmission. The raw triaxial accelerometer data are transferred automatically to a secure web server (Capital Region, Denmark) via the smartphone. During each assessment the participants will fill in a daily report of their resting and sleeping time in order to isolate their sitting time from sleeping time. After the seven-day assessment period the participants will remove the sensor and keep it until the next appointment at Bispebjerg Hospital, where they will return it to the project nurse.

Data collection from feasibility and acceptability

Regarding data on feasibility and acceptability, the intervention leader (TT) will document all components of the recruitment and screening procedure. This will include documentation of the number of invited and screened patients and reasons for exclusion or declining study participation. Acceptability and fidelity to the intervention elements and outcome assessments will be evaluated through interviews with project staff delivering the intervention and with five study participants. Furthermore, this will be monitored using a log sheet in which information on intervention progress and retention will be registered.

Data management

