All data in the feasibility study will be collected and managed using an electronic case record form (eCRF), which is based on REDCap (Research Electronic Data Capture) (29), hosted at the Capital Region, Denmark. REDCap is a secure, web-based application designed to support data capture for research studies, providing 1) an intuitive interface for validated data entry, 2) audit trails for tracking data manipulation and export procedures, 3) automated export procedures for seamless data downloads to common statistical packages and 4) procedures for importing data from external sources. Center for Clinical Research and Prevention, Bispebjerg and Frederiksberg Hospitals, will act as the project owner in REDCap. All access to the server and other server maintenances will be logged. Study setup and hosting will be performed by Bispebjerg Hospital. Only authorized access to the eCRF will be possible using encrypted username and password. Roles in the system are given according to functions (project leader, study nurse etc.). All tasks performed in the eCRF are logged in an audit trail. The project leaders and authorized project staff can add data to the eCRF and will keep the eCRF current to reflect subject status during the study period. The project personnel will make a separate confidential record of personalized details (name and initials) and enrollment log on the individual participant, which is kept separately from the eCRF. Once the eCRF for a participant is completed, the authorized staff will approve the data using an electronic signature and thereby confirm the accuracy of the data recorded.

(Statistical) analyses

The primary analyses will be of feasibility outcomes. We will report the numbers of screened and eligible participants seen over the recruitment period, and the rates of retention and adherence, that is proportion of participants completing outcome assessments and receiving intervention elements (both basic and optional elements). In addition, we will ascertain data completeness of the instruments and any potential bias in the completion of follow-up data to inform the choice of instruments in a future randomized controlled trial. Also, we will use the results (standard deviations) from the objectively measured physical activity levels to determine the appropriate sample size for the later randomized controlled trial.

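### Are refusals at the clinic stage left uncounted, and recruitment left without a rate?

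*Combined protocol and SAP*

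**What the plan says.** The Recruitment section gives the first contact to the clinic: "Patients will be identified and invited by nurses and physicians at the outpatient clinic". Handover to the intervention leader or the project nurse is conditional: "If identified patients are willing and eligible to participate", their contact details are passed on.

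Under Data collection from feasibility and acceptability, the intervention leader is made responsible for documenting every part of recruitment and screening. The plan adds: "This will include documentation of the number of invited and screened patients and reasons for exclusion or declining study participation". The same section plans "interviews with project staff delivering the intervention and with five study participants", to evaluate acceptability and fidelity.

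The (Statistical) analyses section makes feasibility the primary analysis. For recruitment it states: "We will report the numbers of screened and eligible participants seen over the recruitment period". It names rates for retention and adherence only.

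Three further places bear on the point:

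- Design: "Assessment of feasibility will include identification of barriers for recruitment, acceptance of group/randomization status".
- Outcome measures repeats the theme, listing "barriers for recruitment, acceptance of group allocation, study retention".
- Demographic and clinical information says that researchers' "direct access to the electronic patient records and retrieval of these data will be depended on signed informed consent from the relevant participant".

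**The concern.** The person who must document invitations and refusals meets patients only after clinic staff have filtered them. No duty is written for clinic staff to note those who decline or are ineligible. The log sheet is described as covering intervention progress and retention. The enrolment log is described as covering individual participants. The interviews reach delivery staff and five participants. Record access needs consent, which decliners have not given. Read this way, no stated source reaches a patient who says no in the clinic.

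The analysis section appears to make matters worse. Invited, declined and randomised counts are not carried into it, and neither an uptake proportion nor an accrual rate is listed.

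The planned number randomised is fixed at 30, so the denominator and the elapsed time hold most of the recruitment information. If clinic refusals vanished, uptake would look better than it is, and the later randomised trial could be planned on too hopeful a figure.

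**Working it through.** The plan states no recruitment figure, so there is none to reproduce. The check is mainly a comparison of sections, with two short calculations.

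**1. Does the documentation commitment reach the clinic stage?** Under Recruitment, willingness and eligibility are settled before handover. If the leader's record began at handover, there would be few exclusions left to explain, and the screened and eligible counts would nearly coincide. Yet the data-collection section asks for numbers invited and reasons for exclusion, and the analysis section treats screened and eligible as separate counts. These items make sense only if clinic-stage information is included. The commitment therefore covers that stage. What is unwritten is which form is used and who passes it on.

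**2. Is there a plausible channel?** The Recruitment section describes the project nurse as employed in the gastroenterology department, which is where recruitment takes place. Nothing in the documents prevents that nurse or the clinic staff from passing on anonymous counts.

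**3. Does restricted record access remove a source?** No. The consent condition concerns clinical data such as disease location, surgery and medication. The plan nowhere proposes to find refusals or their reasons in patient records. The next sentence also foresees diagnosis and treatment information being used for screening before consent.

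**4. Is objection to randomisation among decliners a named outcome?** Design and Outcome measures speak of accepting group or randomisation status and group allocation. The natural reading is acceptance of the assigned arm by people already randomised, who can all be observed.

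**5. Can the rates be obtained?** With E eligible patients and M months of recruitment, uptake is 30/E and accrual is 30/M. E is reported, 30 is the planned number, and M is known once recruitment closes.

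For accrual, the inputs come from Time Schedule and the outcome-assessment section: start in October or November 2023, project end on 31 December 2024, follow-up of 20 weeks = 140 days.

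- Latest baseline: 31 December 2024 − 140 days = 13 August 2024.
- Start 1 October 2023: 317 days / 30.4375 = 10.4 months; 30/10.4 = 2.9 per month.
- Start 30 November 2023: 257 days / 30.4375 = 8.4 months; 30/8.4 = 3.6 per month.

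These are minimum rates, because they leave no time for analysis and writing before project end.

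**6. What if the clinic kept no tally at all?** If a share f of eligible patients approached declined unlogged, uptake would be overstated by 1/(1 − f). Both f and a figure of 40 referred patients are assumptions. The logged uptake would be 30/40 = 75% (exact 95% CI 59–87%).

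| Assumed f | Factor 1/(1 − f) | Approached, 40/(1 − f) | True uptake (exact 95% CI) |
|---|---|---|---|
| 0% | 1.00 | 40 | 75% (59–87%) |
| 10% | 1.11 | 44 | 30/44 = 68% (52–81%) |
| 30% | 1.43 | 57 | 30/57 = 53% (39–66%) |
| 50% | 2.00 | 80 | 30/80 = 38% (27–49%) |

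The intervals treat the denominator as fixed although the design fixes the 30; the numerical effect is small. Every row below the first requires the team to depart from its own documentation commitment.

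**The case for a change.** The strongest counter-argument is that a commitment with an owner but no route can fail quietly. A refusal not noted on the day is hard to recover, and a busy clinic may not note it unless told to. A rate computed afterwards from eligible patients would carry the same error if eligibility were counted only after referral. The remedy would also be cheap: an anonymous tally and a few sentences.

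Part of this stands. No sentence says how clinic counts reach the leader, and the analysis section does not repeat the invited and declined items. Spelling both out would be tidier.

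The rest does not carry. Silence about a form is not evidence that no tally will be kept, and the harm arises only if the written commitment is not followed. Counting eligibility only after referral would also contradict that commitment. Refusals after referral are visible to the leader and project nurse in any case, and no treatment comparison is touched.

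**Conclusion.** No change to the plan is needed. The data-collection section already asks for the right counts and reasons and names who is responsible. Followed as written, it gives an undistorted denominator and zero overstatement. Uptake and accrual are simple quotients of quantities that will be known, so listing them separately would improve presentation without adding information. The factors of 1.11 to 2.0 describe a failure of conduct under assumed refusal shares, not a fault in the design.

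The conclusion rests on two assumptions: that the leader's commitment covers invitations made by clinic staff, which is the only reading that fits its listed items, and that the team sets up ordinary screening-log practice before the first invitation. The remaining gap is operational and reporting detail that a feasibility team would fill in the normal course.

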Descriptive statistics in the feasibility study will give insight into participants' characteristics as well as distributions and indications of change in the outcome measures. The descriptive statistics will summarize categorical data (frequencies (%)) and continuous data (medians, means (M) and standard deviations (SD)). Changes in outcome measures from baseline to end of intervention will be reported as within-group differences (M and SD) in the intervention and the control group separately and between-group differences in change will be summarized (M, SD). All analyses will be conducted using SAS software (v. 9.3; SAS Institute Inc., Cary, NC, USA).

Risks and adverse events

The SENS motion activity sensor is sealed and placed in a small patch to avoid direct contact with the skin. The participants will be encouraged to change the location of the unit or contact intervention leader (TT) if the patch comes off or if they experience skin redness or itching. In our previous studies using activity monitors on patients with rheumatoid arthritis, few cases of redness and itching were reported as the only adverse events from using the monitors along with the inconvenience of having the unit attached to thigh and/or shoulder (17). Adverse effects such as muscle soreness, joint pain, muscle cramps and increased need to rest may be expected as participants are encouraged to be more physically active. Routine stool and blood samples are included in the study. The blood samples are taken by experienced staff and carried out in a quiet shielded room. A foreseeable risk involves the possible discomfort and small hematoma following the sampling of blood from the antecubital vein.

Ethical considerations

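### The between-group difference in change is to be summarised with an undefined SD and no interval; a baseline-adjusted mean difference with a 95% CI would be a cheap, minor improvement

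*Combined protocol and SAP*

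**What the plan says.** The (Statistical) analyses section puts feasibility first: "The primary analyses will be of feasibility outcomes". Outcome data are summarised descriptively, to show "distributions and indications of change in the outcome measures". For each arm, "Changes in outcome measures from baseline to end of intervention will be reported as within-group differences (M and SD", and then "between-group differences in change will be summarized (M, SD", with no further definition. No section mentions a confidence interval, a standard error or a baseline-adjusted model for the outcome measures.

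Under Randomization and blinding, "Study participants will be randomly assigned (1:1) to either an intervention group (n=15) or a control group (n=15". Under Data collection from outcome assessments, "Outcome assessment will be conducted at study inclusion/baseline and repeated at end of the intervention period", 20 weeks later. The Control group section expects the same assessments of both arms. The later trial will be sized from a different quantity: "we will use the results (standard deviations) from the objectively measured physical activity levels to determine the appropriate sample size".

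**The concern.** Within an arm, each participant has a change, so a mean and SD of change are well defined. Between two independent arms, no participant has a difference. Each outcome gives a single contrast, and a single number has no sample SD. The analyst must therefore choose a meaning for the label, and two analysts could print different figures from the same data.

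Whichever of the two true SDs is chosen, it describes spread among individuals and not the uncertainty of the contrast. This is the only between-arm outcome estimate that the plan describes. With so few participants its imprecision is the main thing a reader needs to see, and the plan does not commit to showing it. The baseline value also enters only by subtraction. That is valid, but for most plausible correlations it leaves some precision unused and lets a chance baseline difference carry through to the contrast.

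**Working it through.** The plan gives no SD, correlation, dropout rate or power calculation for these outcomes, so there is no stated figure to reproduce. Taken from the plan: 15 per arm, with baseline and 20-week values in both arms. Assumed for illustration: baseline/follow-up correlation r from 0.3 to 0.9, equal variances unless stated, and 12 completers per arm as an alternative.

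**1. What the SD could mean.** Let s be a common SD of change, with 15 per arm.
- Pooled SD: s.
- Root-sum-of-squares SD: √(s² + s²) = 1.414 s.
- Standard error of the difference: s√(2/15) = 0.365 s.

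The two true SDs differ by a factor of 1.41. The largest and smallest readings differ by 1.414/0.365 = 3.87.

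**2. Unadjusted precision.** Half-width = t(0.975, 2n−2) × √(2/n) × SD of change.
- 15 per arm: 2.048 × 0.365 = 0.748 SD of change.
- 12 per arm: 2.074 × 0.408 = 0.847 SD of change.

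**3. Baseline adjustment.** With outcome SD σ, the SD of change is σ√(2(1−r)) and the residual SD after regression on baseline is σ√(1−r²). Estimating the slope multiplies the variance by (N−3)/(N−4), where N is the total number analysed. The variance ratio, adjusted to change score, is therefore (1+r)/2 × (N−3)/(N−4). For N = 30 the last factor is 27/26. Half-widths below are in outcome SDs and use 28 and 27 degrees of freedom.

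| r | Variance ratio | Fall in SE | Half-width, change score | Half-width, adjusted |
|---|---|---|---|---|
| 0.3 | 0.675 | 17.8% | 0.885 | 0.728 |
| 0.5 | 0.779 | 11.7% | 0.748 | 0.661 |
| 0.7 | 0.883 | 6.0% | 0.579 | 0.545 |
| 0.8 | 0.935 | 3.3% | 0.473 | 0.458 |
| 0.9 | 0.987 | 0.7% | 0.335 | 0.333 |

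At 12 per arm the falls for r = 0.3, 0.5 and 0.7 are 17.4%, 11.3% and 5.5%. Simulation with independent normal data at 15 per arm gave the same half-width ratios as the formula for r = 0.3 to 0.8 (0.823, 0.884, 0.941, 0.968).

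**4. Where the gain becomes a loss.** Setting (1+r)/2 × 27/26 = 1 gives r = 52/27 − 1 = 0.926. At 12 per arm it is 40/21 − 1 = 0.905. Beyond that, adjustment costs a little: 0.6% of the SE at r = 0.95, with a ceiling of √(27/26) − 1 = 1.9% as r approaches 1. Unequal variances can do the same. With r = 0.7 and a 20-week SD 1.3 times baseline (assumed), the variance of change is 1 + 1.69 − 1.82 = 0.87 and the residual variance is 1.69 × 0.51 = 0.862. The ratio is 0.862/0.87 × 27/26 = 1.029, so the SE is 1.4% larger (2.0% at 12 per arm).

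**5. Chance baseline imbalance.** For any one outcome, the probability that the arms differ at baseline by more than 0.5 SD is 2(1 − Φ(0.5/0.365)) = 17%; at 12 per arm, 2(1 − Φ(0.5/0.408)) = 22%. An imbalance of 0.5 SD shifts the change-score contrast by (1−r) × 0.5 = 0.35, 0.25 or 0.15 SD at r = 0.3, 0.5 or 0.7. Regression on baseline removes this shift.

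**6. Number of intervals.** A count of continuous outcomes from the Outcome measures subsections:
- activity sensor 7, self-reported activity and sitting 5;
- self-efficacy 1, quality-of-life domains 4, fatigue dimensions 5, pain 1, anxiety and depression 2, calprotectin 1;
- lipids 5, CRP, albumin and HbA1c 3, blood pressure 2 (systolic and diastolic assumed), anthropometry 5.

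The total is about 41. If there were no effect at all, 0.05 × 41 ≈ 2 intervals would be expected to exclude zero.

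**The case against.** The strongest reply is that this is a descriptive summary in a feasibility study, and no decision in the protocol rests on it. That is correct and sets the severity. The per-arm SDs of change will stand beside the third figure, so a reader could often work out which meaning was used, and could rebuild an unadjusted interval if n per arm is given. The adjusted estimate could be rebuilt only if means and SDs at baseline, at 20 weeks and of change were all given per arm for the same participants, which the plan does not promise. Labelling the SD and adding an unadjusted interval would cure the two plain defects; adjustment is a further improvement. Its gain is modest, nearly nil for very stable outcomes, and can turn into a slight loss.

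A second reply also stands. The Intervention section lets intervention participants team up as exercise partners, and everyone in that arm shares a group session. Outcomes of partners may be correlated, and an ordinary regression interval would then be too narrow. An unadjusted interval has the same weakness.

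A reader might infer more than the documents support:
- **That the comparison is biased.** It is not: under randomisation the difference in mean change is unbiased.
- **That the later trial would be wrongly sized.** The plan sizes it from SDs of measured activity levels, not from this between-group SD.
- **That hypothesis tests are missing.** Leaving them out suits a feasibility study.

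**Conclusion.** The point holds as a minor, inexpensive improvement. The between-group SD is undefined, with readings from 0.365 to 1.414 times the SD of change at 15 per arm. The unadjusted 95% interval that goes unreported extends about 0.75 SD of change either side.

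Baseline adjustment would cut the standard error by about 18% to 1% for r from 0.3 to 0.9, with a loss of about 1% possible for very stable outcomes or unequal variances. It also removes the effect of chance baseline imbalance. These sizes rest on assumed correlations, equal variances except where stated, and independent participants; the documents give no figures for any of these. Feasibility results and the sizing of the later trial are untouched.

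**What to change.** In the (Statistical) analyses section, keep the within-arm mean and SD, label the latter as the SD of change, and give n per arm for each outcome. Replace the between-group mean and SD with wording such as:

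> For each continuous outcome, the between-group mean difference at 20 weeks will be estimated by linear regression of the 20-week value on arm and baseline value, in participants with both values and without imputation, and reported with its 95% CI and n per arm. These estimates are exploratory. No hypothesis tests will be done, and an interval that excludes zero will not be read as evidence of efficacy. Intervals assume independent participants and may be too narrow if outcomes of exercise partners are correlated.

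Using change as the response gives the same arm coefficient, because subtracting baseline only lowers the baseline coefficient by one. The result is therefore still a between-group difference in change.

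The cost is a few sentences, a few lines of SAS and one residual degree of freedom (27 instead of 28), with no extra data. The downside is many wide intervals, of which about 2 in 41 would exclude zero by chance if there were no effect; hence the exploratory label. Complete-case estimates share any follow-up bias, which the plan already intends to examine: "we will ascertain data completeness of the instruments and any potential bias in the completion of follow-up data".
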